## 16.3 Data Handling and Derivation of Product Use Pattern

### Categories

Only available data collected since the first day after randomization (Day 2) up until V16 (Day V16 excluded) will be considered for product use categorization for product use pattern categorization.

It is expected that any duplicate product use record (i.e. more records on the same study day) is identified during data review and flagged for the exclusion from the analysis.

#### 16.3.1 Preliminary Data Handling

The following data handling will be performed on the two 6-month analysis periods separately.

The following data of the product use diary will not be considered for product use categorization and will be set to missing:

- Records of days with reported CC use for subjects in the THS 2.2 arm who report CC use for less than 5 days in total.
- Records of days with reported THS use for subjects in the CC arm who report THS 2.2 use for less than 5 days in total
- Records of days with outliers in any of the product use, identified as those values which are above 60 units and also greater than  $\text{median} + 3 * \text{IQR}$ , with IQR being the inter-quartile range of the specific product use data distribution.

Missing dates for Visits 5, 6, 7, 8, 9, 10, 11, 12, 13, 14, 15 and 16 will be imputed for the calculation of product use exposure within periods by selecting the middle date between two non-missing visits. For example, if Visit 6 and Visit 7 are missing, then take the number of days between Visit 5 and Visit 8 and divide by 3 and round to the nearest day. Add this resulting number of days to Visit 5 to determine the Visit 6 imputed study day and then add this resulting number of days to Visit 6 to determine the Visit 7 imputed study day. For an early terminated subject, add 30 days after the last visit to determine each successive visit's study day.

Missing data will be interpolated using a moving average over a 15-day window ( $\pm 7$  days) centered on the missing data. For example, someone missing THS data on Day 10 would have the average of non-missing values between Days 3 to 17 interpolated for Day 10.

### 16.3.2 Derivation of Actual Product Use Categories

Per-Day product use categories will be derived for each study day as indicated in Table 19, and the percent of days (over the whole analysis period) the subjects fall in each category will be computed.

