#### **12.7.1.3.4 Missing Product Use Sensitivity Analysis**

A Missing product use sensitivity analysis will be produced for the FAS-EX population using a 95% CI and 2-sided p-value to compare THS-use versus CC-use, by re-analyzing the primary endpoints re-classifying all subjects based on the available data in the diary (Table 15.2.3.1.2) with no imputation (see Section 16.3.2).

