**Table 19: Per Day Actual Product Use Pattern Categories**

Category Label	Definition
THS-use	$nTHS + nCC \geq 1$ and $nECig/(nTHS+nCC+nECig+nOtherTob) < 50\%$ and $nOtherTob/(nTHS+nCC+nECig+nOtherTob) < 50\%$ and $nTHS/(nTHS + nCC) \geq 70\%$
Dual-use	$nTHS + nCC \geq 1$ and $nECig/(nTHS+nCC+nECig+nOtherTob) < 50\%$ and $nOtherTob/(nTHS+nCC+nECig+nOtherTob) < 50\%$ and $1\% \leq nTHS/(nTHS + nCC) < 70\%$
CC-use	$nTHS + nCC \geq 1$ and $nECig/(nTHS+nCC+nECig+nOtherTob) < 50\%$ and $nOtherTob/(nTHS+nCC+nECig+nOtherTob) < 50\%$ and $nTHS/(nTHS + nCC) < 1\%$
ECig-use	1) $nTHS + nCC \geq 1$ and $nECig \geq nOtherTob$ and $[nECig/(nTHS+nCC+nECig+nOtherTob) \geq 50\%$ or $nOtherTob/(nTHS+nCC+nECig+nOtherTob) \geq 50\%]$ ; or 2) $nTHS + nCC < 1$ and $nECig \geq nOtherTob$ and $(nECig \geq 1$ or $nOtherTob \geq 1)$
OtherTobacco-use	1) $nTHS + nCC \geq 1$ and $nECig < nOtherTob$ and $[nECig/(nTHS+nCC+nECig+nOtherTob) \geq 50\%$ or $nOtherTob/(nTHS+nCC+nECig+nOtherTob) \geq 50\%]$ ; or 2) $nTHS + nCC < 1$ and $nECig < nOtherTob$ and $(nECig \geq 1$ or $nOtherTob \geq 1)$
Abstainer	$nTHS + nCC < 1$ and $nECig < 1$ and $nOtherTob < 1$
Missing	Missing product use data

Note: nTHS, nCC, nECig, nOtherTob indicates the quantity of daily product use reported respectively for THS 2.2, CC, E-cigarette, and other tobacco..

The product use categories for the 3-month analysis periods (J[V4, V7], J[V7, V10], [V10, V13], J[V13, V16]) are derived following the same rules defined for per-day categories in Table 19, but using the average product use over the 3-month period. In addition:

- In order to factor in the higher relevance of later product use in the period for their impact on the endpoints, a weighted average approach is adopted, using the day number as weighting factor. The day numbers will be relative to the analysis period (i.e. weights ranging between 1 and the last day number of the period, normalized to

the total sum of the weights).

- THS-use or CC-use categories will be assigned to the analysis period when consistently observed on a per-day basis over the same period. In particular the frequency of THS-use and of CC-use per-day categories is calculated using the same weighting scheme previously adopted to compute the average product use over the entire 3-month period. THS-use and CC-use product use categories would be turned into Dual-use category if the weighted percent of days in respectively THS-use and CC-use is less than 50% during the analysis period.

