- Subjects in the THS-use category will be flagged as Exclusive-use if  $n_{\text{THS}}/(n_{\text{THS}} + n_{\text{CC}}) \geq 95\%$ . Subjects in CC-use will be flagged as Exclusive-use if  $n_{\text{THS}}/(n_{\text{THS}} + n_{\text{CC}}) \leq 5\%$ .
- Setting to Missing the product use categories if, after the interpolation, more than one third of the days (e.g. 30 days for the 3-month periods) of missing product use category during the analysis period. For the sensitivity analysis on missing product use data (see Section 12.7.1.3.4), the non-imputed product use category will be defined based on the available data (i.e. categories will be set to Missing only if no data is recorded for the analysis period).

The product use categories for the six-month ]V4,V10[ and [V10,V16[ analysis periods are derived following the same approach used for the 3-month periods, with the following differences:

- A weighting scheme for the calculation of the average of the product use over the 6-month period is adopted so to reflect the increasing relevance of the product use over time for their association with the value of the endpoints at the end of the period and especially during the last 3 months. To this aim, before being normalized the weights are set as follows:
  - Set to 1.0 for the ]V4, V7] and [V10, V13] parts of each 6-month analysis period
  - Range between 1.0 up until the last study day relative to the ]V7, V10[ and ]V13, V16[ time window, for the last 3-months of each 6-month analysis period.
- For each 6-month period, subjects having product use categories different between the two 3-months period components will move to a category with label “Switcher” if:

- Category is THS-use in one 3-month sub-period, and different from Dual-use (either CC-use or Other-use) in the other sub-period
- Category is CC-use or ECig-use or OtherTobacco-use or Abstainer in only one of the 3-month sub-periods
- For analysis purposes, an over-arching category with label “Other-use” will be used to incorporate all product use categories different from THS-use, Dual-use, or CC-use. The detailed categories will be used only for the descriptive summaries of the product use over time.
- Setting to Missing the category if at least one of the categories derived for the two 3-month sub-periods is missing, apart from:
  - If ]V7, V10[ category is Missing when the subjects early terminate after V7 and category of ]V4, V7[ is not missing, the latter will be assigned to ]V4, V10[.

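### As written, the 50%-of-days test counts unrecorded diary days against THS-use and CC-use; late gaps can relabel single-product users, mainly in the no-imputation sensitivity analysis

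*SAP*

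**What the plan says.** SAP 16.3.2 first gives every study day one category (Table 19), and then "the percent of days (over the whole analysis period) the subjects fall in each category will be computed". One row of Table 19 is Missing, defined as "Missing product use data". SAP Table 1 and Protocol Table 7 likewise express the 50% condition in days of the analysis period.

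For a 3-month period the day number is the weight, with "weights ranging between 1 and the last day number of the period, normalized to" the sum of the weights. THS-use or CC-use turns into Dual-use "if the weighted percent of days in respectively THS-use and CC-use is less than 50% during the analysis period". For a 6-month period the weights are "Set to 1.0 for the ]V4, V7] and [V10, V13] parts of each 6-month analysis period" and rise day by day through the last three months.

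Gaps are first interpolated from values within 7 days on either side, separately in each 6-month period (SAP 16.3.1). The category is then set to Missing for "more than one third of the days (e.g. 30 days for the 3-month periods) of missing product use category". In the sensitivity analysis of SAP 12.7.1.3.4 there is no imputation and the limit is lifted: "the non-imputed product use category will be defined based on the available data", the aim being "re-classifying all subjects based on the available data in the diary".

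**The concern.** A day with no data says nothing about which product was used. If it stays in the denominator, it acts as evidence against THS-use and against CC-use, and the only outcome of failing the test is Dual-use. Someone who reported nothing but THS 2.2, or nothing but cigarettes, can then lose the matching category because of diary completeness rather than product use.

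The primary contrast is THS-use versus CC-use, and Dual-use versus CC-use is also reported. Relabelling would take single-product users out of the first contrast and could place exclusive THS users in the Dual-use group of the second. The sensitivity analysis is meant to show whether missing diary data matter, so it should not itself penalize missing days.

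**Working it through.** **Inputs.** Nominal visit days (SAP Table 17): V4 day 1, V7 day 92, V10 day 183, V13 day 274, V16 day 365. With the SAP's brackets, the four 3-month periods have 91, 90, 92 and 90 days.

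**The plan's own figure.** One third of 90, 91 and 92 days is 30.0, 30.3 and 30.7. So 30 residual missing days are allowed and 31 are not, which matches the SAP's example of 30.

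**Formula.** Take a subject in one category on every classified day, with m residual missing days at the end of an L-day period.
- 3-month share = (L−m)(L−m+1) / [L(L+1)]
- 6-month share = [L1 + (L2−m)(L2−m+1)/2] / [L1 + L2(L2+1)/2]

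**Main analysis, period ending at V10 (L1 = 91, L2 = 90).**

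| m | 3-month share | 6-month share |
|---|---|---|
| 26 | 4160/8190 = 50.8% | 2171/4186 = 51.9% |
| 27 | 4032/8190 = 49.2% | 2107/4186 = 50.3% |
| 28 | 3906/8190 = 47.7% | 2044/4186 = 48.8% |
| 30 | 3660/8190 = 44.7% | 1921/4186 = 45.9% |
| 31 | set to Missing | – |

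The period ending at V16 behaves the same way. Interpolation reaches 7 days past the last record, so m = 27 to 30 is a raw gap of 34 to 37 days running to V10 or V16.

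**Which label results.**
- CC-only, m = 27 to 30: the last 3-month period becomes Dual-use. CC-use then holds in only one sub-period, which gives Switcher, hence Other-use.
- THS-only, m = 28 to 30: the 6-month test fails too, and the subject is Dual-use. At m = 27 the 6-month category remains THS-use, because THS-use beside Dual-use is not a Switcher pattern.

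**What drives it.** Without day weights the share at the limit is 60/90 = 66.7%, which passes. A 30-day gap at the start of the period leaves 1 − 930/8190 = 88.6%, which also passes. Failure needs the weights and a late gap.

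**Shorter late gaps raise the threshold (L = 91, weight sum 4186, half of it 2093).** With 15 trailing days missing, the recorded weight is 76×77/2 = 2926, so 2093/2926 = 71.5% of it must be THS-use or CC-use. With 20 missing it is 71×72/2 = 2556, so 81.9%.

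**No-imputation sensitivity analysis.** SAP 16.3.1 places each later visit of an early terminator 30 days after the one before. Assume a complete single-product diary to the last visit.
- Last visit V15 (day 337): V16 is imputed at day 367, so the period is days 275 to 366, or 92 days, with 63 recorded. Share = 63×64/(92×93) = 4032/8556 = 47.1%; the 6-month share is (92+2016)/(92+4278) = 48.2%. Both fail. In the main analysis interpolation gives 70 days: 4970/8556 = 58.1%, which passes.
- Last visit V14 (day 302): V16 is imputed at day 362, so the period has 87 days with 28 recorded. Share = 28×29/(87×88) = 812/7656 = 10.6%, which fails. In the main analysis 87 − 35 = 52 days remain missing, so the sub-period is Missing and the [V10, V13] category is carried forward: the subject stays THS-use or CC-use.
- Diary stops at V15 but V16 is attended on day 365: 63 of 90 days, 4032/8190 = 49.2%, which fails. The main analysis gives 4970/8190 = 60.7%, which passes.

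**The case against.** **The denominator is inferred.** The whole-period phrase could name the time span only. SAP 16.3 says that only available data are considered, and the sensitivity analysis is said to rest on available data. The day frequency also shares its weighting scheme with the average product use, and an average can only be taken over days with a value. This stands as a real alternative reading. But none of these places states a denominator, and the literal text with the Missing row points the other way. Two programmers could build different primary groups.

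**The main-analysis window is a few days wide.** This also stands. One more missing day sets the category to Missing, which takes most such subjects out of the contrast anyway. A gap ending at V7 or V13 with the diary resumed at once is partly filled from the later side: in the 91-day period a 30-day residual gap ending 7 days early scores 2101/4186 = 50.2% and passes.

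**Use shortly before the visit matters most.** The SAP weights late use deliberately, and five unrecorded weeks before V16 leave exposure unknown when it counts. That is an argument for a data-sufficiency rule, which the one-third limit already is. It is not an argument for calling the subject a dual user.

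**Stronger readings to avoid.** A reader might infer that the whole-period denominator alone misclassifies subjects in the main analysis, or that the sensitivity analysis sends most sparse diaries to Dual-use. The first is refuted by the 66.7% and 88.6% above. The second has no support: the documents give no distribution of diary gaps, and a CC-only subject who fails in one sub-period becomes Switcher, not Dual-use.

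**Conclusion.** The point holds on the literal wording, with limited reach in the main analysis and wider reach in the no-imputation sensitivity analysis. There, single-product subjects whom the main analysis keeps can be removed, so the run does not do what it states.

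The figures assume nominal visit days; the ±5-day visit windows shift the thresholds slightly (a 92-day period needs 28 missing days rather than 27). For early terminators the new label has little effect on the V16 estimate, because most have no V16 measurement and their V7 and V10 data follow the ]V4, V10[ category. Subjects who stop the diary but attend V16 carry the effect into the estimate.

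How many subjects are affected cannot be computed from the documents. The issue is misclassification, not precision. With 475×0.65×0.8×0.6 = 148 THS-use and 475×0.65×0.8 = 247 CC-use subjects and SD 6.4, the FEV1 half-width is 1.30 %pred. It would be 1.37 if 10% of both groups were relabelled (an assumed figure), still within the planned 1.5.

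**What to change.** In SAP 16.3.2, define the percentage over the days of the analysis period that have a non-missing per-day category, with weights re-normalized over those days. Count reported or interpolated days in the main analysis and reported days only in the no-imputation run. Apply this to the 3-month and 6-month rules. Keep the one-third rule as the data-sufficiency test in the main analysis. A subject in THS-use, or in CC-use, on every classified day then scores 100%, whatever the gap.

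The cost is one sentence and a small change in derivation code before database lock, with two downsides. Some subjects with late gaps are classified on fewer days. And ]V4, V10[ categories could differ from those of the original study, with which SAP section 9 seeks consistency. If those must stay identical, apply the change to [V10, V16[ and to the sensitivity run only. Either way, report how many subjects change category. If recorded days were always intended, the sentence only makes that explicit.

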**Table 19: Per Day Actual Product Use Pattern Categories**

Category Label	Definition
THS-use	$nTHS + nCC \geq 1$ and $nECig/(nTHS+nCC+nECig+nOtherTob) < 50\%$ and $nOtherTob/(nTHS+nCC+nECig+nOtherTob) < 50\%$ and $nTHS/(nTHS + nCC) \geq 70\%$
Dual-use	$nTHS + nCC \geq 1$ and $nECig/(nTHS+nCC+nECig+nOtherTob) < 50\%$ and $nOtherTob/(nTHS+nCC+nECig+nOtherTob) < 50\%$ and $1\% \leq nTHS/(nTHS + nCC) < 70\%$
CC-use	$nTHS + nCC \geq 1$ and $nECig/(nTHS+nCC+nECig+nOtherTob) < 50\%$ and $nOtherTob/(nTHS+nCC+nECig+nOtherTob) < 50\%$ and $nTHS/(nTHS + nCC) < 1\%$
ECig-use	1) $nTHS + nCC \geq 1$ and $nECig \geq nOtherTob$ and $[nECig/(nTHS+nCC+nECig+nOtherTob) \geq 50\%$ or $nOtherTob/(nTHS+nCC+nECig+nOtherTob) \geq 50\%]$ ; or 2) $nTHS + nCC < 1$ and $nECig \geq nOtherTob$ and $(nECig \geq 1$ or $nOtherTob \geq 1)$
OtherTobacco-use	1) $nTHS + nCC \geq 1$ and $nECig < nOtherTob$ and $[nECig/(nTHS+nCC+nECig+nOtherTob) \geq 50\%$ or $nOtherTob/(nTHS+nCC+nECig+nOtherTob) \geq 50\%]$ ; or 2) $nTHS + nCC < 1$ and $nECig < nOtherTob$ and $(nECig \geq 1$ or $nOtherTob \geq 1)$
Abstainer	$nTHS + nCC < 1$ and $nECig < 1$ and $nOtherTob < 1$
Missing	Missing product use data

Note: nTHS, nCC, nECig, nOtherTob indicates the quantity of daily product use reported respectively for THS 2.2, CC, E-cigarette, and other tobacco..

The product use categories for the 3-month analysis periods (J[V4, V7], J[V7, V10], [V10, V13], J[V13, V16]) are derived following the same rules defined for per-day categories in Table 19, but using the average product use over the 3-month period. In addition:

- In order to factor in the higher relevance of later product use in the period for their impact on the endpoints, a weighted average approach is adopted, using the day number as weighting factor. The day numbers will be relative to the analysis period (i.e. weights ranging between 1 and the last day number of the period, normalized to

the total sum of the weights).

- THS-use or CC-use categories will be assigned to the analysis period when consistently observed on a per-day basis over the same period. In particular the frequency of THS-use and of CC-use per-day categories is calculated using the same weighting scheme previously adopted to compute the average product use over the entire 3-month period. THS-use and CC-use product use categories would be turned into Dual-use category if the weighted percent of days in respectively THS-use and CC-use is less than 50% during the analysis period.
- Subjects in the THS-use category will be flagged as Exclusive-use if  $n_{\text{THS}}/(n_{\text{THS}} + n_{\text{CC}}) \geq 95\%$ . Subjects in CC-use will be flagged as Exclusive-use if  $n_{\text{THS}}/(n_{\text{THS}} + n_{\text{CC}}) \leq 5\%$ .
- Setting to Missing the product use categories if, after the interpolation, more than one third of the days (e.g. 30 days for the 3-month periods) of missing product use category during the analysis period. For the sensitivity analysis on missing product use data (see Section 12.7.1.3.4), the non-imputed product use category will be defined based on the available data (i.e. categories will be set to Missing only if no data is recorded for the analysis period).

The product use categories for the six-month ]V4,V10[ and [V10,V16[ analysis periods are derived following the same approach used for the 3-month periods, with the following differences:

- A weighting scheme for the calculation of the average of the product use over the 6-month period is adopted so to reflect the increasing relevance of the product use over time for their association with the value of the endpoints at the end of the period and especially during the last 3 months. To this aim, before being normalized the weights are set as follows:
  - Set to 1.0 for the ]V4, V7] and [V10, V13] parts of each 6-month analysis period
  - Range between 1.0 up until the last study day relative to the ]V7, V10[ and ]V13, V16[ time window, for the last 3-months of each 6-month analysis period.
- For each 6-month period, subjects having product use categories different between the two 3-months period components will move to a category with label “Switcher” if:

- Category is THS-use in one 3-month sub-period, and different from Dual-use (either CC-use or Other-use) in the other sub-period
- Category is CC-use or ECig-use or OtherTobacco-use or Abstainer in only one of the 3-month sub-periods
- For analysis purposes, an over-arching category with label “Other-use” will be used to incorporate all product use categories different from THS-use, Dual-use, or CC-use. The detailed categories will be used only for the descriptive summaries of the product use over time.
- Setting to Missing the category if at least one of the categories derived for the two 3-month sub-periods is missing, apart from:
  - If ]V7, V10[ category is Missing when the subjects early terminate after V7 and category of ]V4, V7[ is not missing, the latter will be assigned to ]V4, V10[.
  - If ]V13, V16[ category is Missing when the subjects early terminate after V10 and category of [V10, V13] is not missing, the latter will be assigned to [V10, V16[.

For the sensitivity analysis on missing product use data (see Section 12.7.1.3.4), the category will be set to Missing only if the categories of both the two 3-month sub-periods are set to missing, otherwise the category will be set to the non-missing category of the two 3-month sub-periods.

- The product use categories for the 12-month randomized period are derived combining the product use categories derived for the two 6-month periods as reported in Table 20.

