**Table 1: Actual Product Use General Pattern Categories**

Category Label	General Description
Dual-use	
 
• <math>\geq 1</math> THSts or CC and
 
• <math>1\% \leq</math> THSts <math>< 70\%</math> over the entire analysis period or
 
• THS-use and CC-use don't apply due to <math>< 50\%</math> of the days
 

CC-use	
 
• <math>\geq 1</math> THSts or CC and
 
• <math>< 1\%</math> THSts over entire analysis period and
 
• <math>< 1\%</math> THSts on <math>\geq 50\%</math> of the days in analysis period
 

Other-use	General category encompassing subjects with missing product use, or subjects using e-cigarettes or other tobacco products, subjects who quit, or subjects who switched across different use patterns between consecutive analysis periods.

Details of the product use categories are reported in Appendix 16.3 "Data Handling and Derivation of Product Use Pattern Categories". THSts = THS Tobacco Stick; THS=Tobacco Heating System; CC= Conventional Cigarette.

Full details of the product use categories derivation are reported in Appendix 16.3 "Data Handling and Derivation of Product Use Pattern Categories".

General product use categories will be used for both safety summaries and non-safety analysis. More granular product exposure categories will be used for the detailed description of the product use patterns observed in the study.

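### Table 19 tests e-cigarettes and other tobacco separately against 50%, so a sustained user of both, together half or more of all use, can be classed as THS-use, Dual-use or CC-use

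*SAP*

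**What the plan says.** SAP section 16.3.2 builds the exposure categories from Table 19. THS-use, Dual-use and CC-use all require at least one THS stick or cigarette, plus two separate limits on other products:

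- e-cigarettes: "nECig/(nTHS+nCC+nECig+nOtherTob) < 50" (per cent);
- other tobacco: "nOtherTob/(nTHS+nCC+nECig+nOtherTob) < 50" (per cent).

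The three rows are then told apart by the THS share of THS plus CC. THS-use needs "nTHS/(nTHS + nCC) \geq 70" (per cent).

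The rule is carried forward in steps:

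- The 3-month categories are "derived following the same rules defined for per-day categories in Table 19, but using the average product use over the 3-month period".
- A check on days follows: "THS-use and CC-use product use categories would be turned into Dual-use category if the weighted percent of days" in the category is below 50%. The days are themselves classed by Table 19.
- The six-month "analysis periods are derived following the same approach used for the 3-month periods", with different weights, and Table 20 combines them into the 12-month category.

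These categories define exposure in the FAS-EX (SAP 10.2), the primary THS-use versus CC-use contrast (12.7.1.2), entry to the PP population (10.3) and the event in the propensity model (12.7.3.2). SAP Table 1 describes Other-use in general terms as including "subjects using e-cigarettes or other tobacco products". Protocol section 6.2.1 tolerates other tobacco and nicotine products in both arms.

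**The concern.** Two limits of 50% on two separate shares do not limit their sum to 50%; together they allow anything short of 100%. The ECig-use and OtherTobacco-use rows do not close the gap: when any THS or CC is used, they also need one single share to reach 50%. Because the THS share ignores other products, a small number of THS sticks without cigarettes counts as 100% THS.

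The result is not monotone. With 1 THS stick and 2 e-cigarette uses the day is ECig-use. Add 2 uses of other tobacco and the day becomes THS-use, although THS is now a smaller part of the total.

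At stake is the content of the groups in the primary contrast. A subject recorded as THS-use or CC-use may be using mainly neither product.

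**Working it through.** The plan states no figure that depends on this rule, so the check is to apply Table 19 literally. Cases are written (THS, CC, e-cigarette, other tobacco).

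**Formulas.** Total N = sum of the four. E-cigarette share = e-cigarette/N. Other-tobacco share = other tobacco/N. THS share = THS/(THS+CC).

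| Case | E-cig share | Other-tobacco share | Combined | Table 19 | Summed test |
|---|---|---|---|---|---|
| (1,0,2,0) | 2/3 = 67% | 0% | 67% | ECig-use | ECig-use |
| (1,0,2,2) | 2/5 = 40% | 2/5 = 40% | 80% | THS-use | ECig-use |
| (4,0,3,3) | 3/10 = 30% | 3/10 = 30% | 60% | THS-use | ECig-use |
| (2,0,9,9) | 9/20 = 45% | 9/20 = 45% | 90% | THS-use | ECig-use |
| (7,3,9,9) | 9/28 = 32% | 9/28 = 32% | 64% | THS-use | ECig-use |
| (0,1,20,20) | 20/41 = 49% | 20/41 = 49% | 98% | CC-use | ECig-use |
| (5,0,10,0) | 10/15 = 67% | 0% | 67% | ECig-use | ECig-use |
| (5,0,0,10) | 0% | 10/15 = 67% | 67% | OtherTobacco-use | OtherTobacco-use |
| (10,0,9,0) | 9/19 = 47% | 0% | 47% | THS-use | THS-use |

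The last three rows show that use of a single other product is handled alike under both rules.

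**All combinations.** Over all integer values 0 to 20 of the four counts, 37,621 cells are classed THS-use, and 20,840 of them have more than 50% other products. None of the 20,840 involves only one other product type. These are combinations, not expected frequencies of subjects.

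**Carry-through.** A constant (2,0,9,9) user has the same average under any weighting. The 3-month category is THS-use, every day is THS-use so the check on days is passed, the 6-month category is THS-use, and THS-use combined with THS-use in Table 20 gives THS-use at 12 months. The rule beginning "Subjects in the THS-use category will be flagged as Exclusive-use if" has a 95% threshold on THS/(THS+CC). Here 2/(2+0) = 100%, so the flag is set.

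**A branch that cannot operate.** Part 1 of ECig-use asks for e-cigarettes at least equal to other tobacco and for either share to reach 50%. If the other-tobacco share reached 50%, the e-cigarette share would too, leaving 0% for THS and CC, while part 1 requires at least one of these. So the larger-product allocation does nothing for mixed users. With a summed test it would work.

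**After the change.** (THS+CC)/N exceeds 50%, and THS is at least 70% of THS+CC. The lowest THS share of all products in THS-use is then just above 0.70 × 50% = 35%, where the current rule lets it approach 0%.

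**The case against.** A reader might infer that anyone using mainly other products enters THS-use. The documents do not support that. One dominant other product sends the subject to ECig-use or OtherTobacco-use, hence to Other-use. The gap needs both product types.

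Nor is one odd day enough. The pattern has to dominate the weighted averages and survive the check on days, the Switcher rules and Table 20. Someone who alternates between e-cigarette-dominated and other-tobacco-dominated days would fail the check on days for THS-use and go to Dual-use. Subjects are also instructed to use the allocated product exclusively (protocol 6.2.1), and nothing suggests that sustained three-way use is common. This stands and limits the point.

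A reader might also see a contradiction with Table 1. That is too strong. Table 1 is a general description that refers to Appendix 16.3. Read literally, it would move every e-cigarette or other-tobacco user to Other-use, which a summed 50% test would not do either. Where the cut-off lies is a design choice. The THS+CC denominator is stated openly in both documents and is not in itself an error.

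Finally, it is tempting to say that total NNAL or total NNN would be distorted in a known way. The documents give no content of these for other products, the gap affects both sides of the contrast, and the shares are of counts, not of exposure.

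Existing analyses help only in part. Other-product use is summarised and listed (SAP 12.7.2.1), and the FAS-AR analysis (12.7.1.3.2) does not use the categories. Product adherence (6.3.3, Table 13) counts only THS and CC, and none of the analyses in 12.7.1.3.1 to 12.7.1.3.7 specifically identifies or removes these subjects from the as-exposed contrast or the PP set.

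**Conclusion.** The point holds in a narrow form. Table 19 classes as THS-use, Dual-use or CC-use a subject who uses both e-cigarettes and other tobacco, each below 50% of all products but together 50% or more. Later steps reuse the same rule and do not correct sustained mixed use, so such a subject can reach the primary contrast and the PP population. Within THS-use the combined share of other products can approach 100%.

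This rests on a literal reading of Table 19. How many subjects are affected is not known and is probably few. No size or direction of bias is claimed. It is a low-priority correction to a stated rule.

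**What to change.** In the THS-use, Dual-use and CC-use rows of Table 19, replace the two conditions by one: (nECig + nOtherTob)/(nTHS + nCC + nECig + nOtherTob) < 50%. In part 1 of the ECig-use and OtherTobacco-use rows, use the complement (≥ 50%) and keep the existing allocation to whichever product is larger. State the unit in which e-cigarette use is counted.

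The work is a small edit to Table 19 and the derivation program. The diary data are already collected, and SAP section 3 allows amendments before database lock. There are two small costs. Some 6-month categories could differ from those of the original study, and SAP section 9 gives consistency with that study as a reason for using 6-month categories. The sum also leans harder on the undefined e-cigarette unit: if uses are counted in small units, genuine THS users could be pushed into Other-use.

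If alignment with the original study must be kept, retain the current rule and add a sensitivity analysis of the primary endpoints with subjects reclassified by the summed test, reporting how many change category.
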